### 6. SAMPLE SIZE AND POWER CONSIDERATIONS

The sample size for this study is not based on a formal statistical calculation since this is an exploratory clinical study for a rare disease and no formal data is available to support estimation for the primary endpoint. However, a sample size of 34 subjects per treatment group is considered to be adequate to meet the objectives of the study.

### 7. STATISTICAL METHODOLOGY

#### 7.1 Blinded Data Review

Prior to database lock, a blinded data review meeting (BDRM) will be conducted. Protocol deviations, protocol defined analysis populations will be confirmed during the meeting. Additional data handling rules may be introduced as results of data review. Should additional data handling rules be confirmed during the meeting, they will be incorporated into the analyses planned in this SAP.

PK data that are considered "invalid" will be flagged in the listing. The PK data handling will be assessed during BDRM prior to database lock and in the investigation of PK data handling assessment after unblinding. A separate PK data handling document will be produced to cover both pre- and post- unblinding decisions. If PK sample handling errors or other factors are identified after data unblinding, and these errors have led to unexpected erroneous data, then these erroneous data will be regarded as "invalid".

#### 7.2 Disposition of Subjects

The number of subjects who completed or prematurely discontinued from the study, the reasons for discontinuation, and the number of subjects in each analysis population will be summarized by treatment group.

The number of subjects who enter screening will be summarized, and the percentage of these subjects who fail to meet entry criteria will be reported for total subjects. Screen failures will be summarized in total and by each reason for screen failure.

The data listing for Subject disposition will be generated.

### **7.3 Demographic and Other Baseline Characteristics**

The subject demographic and baseline characteristic will be summarized by treatment in table and presented in data listing for the ITT population.

### **7.4 Medical History**

The subjects Medical and surgical history will be summarized by treatment, SOC and PT in table and presented in data listing for the safety population.

The number and percentage of subjects who had at least one medical history or surgical history will be presented. For each medical history or surgical history term the count and percentage of subjects will be presented.

In the above tables, SOC is sorted by International order; then within SOC, PT is sorted by descending counts under Overall Total column, then descending counts under Placebo column, then alphabetic order for PTs with the same count.

### **7.5 Prior or Concomitant Medications**

The prior and concomitant medications will be summarized in table separately by treatment group and presented in data listing for the SAF population. The data will be coded using World Health Organization Drug Dictionary (WHO-DD). The summaries will be by ATC level 2 and preferred name and treatment.

The number and percentage of subjects who had at least one prior or concomitant medication will be presented. For each prior or concomitant medication term, the number and percentage of subjects will be presented.

### **7.6 Fitzpatrick skin scale test**

Fitzpatrick scale test will be summarized in table by treatment and visit.

The Fitzpatrick skin type will be summarized with number and percentage and the Fitzpatrick total score will be summarized with descriptive statistics (N, mean, SD, median, minimum, and maximum).

### **7.7 Prohibited medication**

The prohibited medications coded by the protocol Appendix 1 Table 14.1-1 will be summarized in table by treatment and presented in data listing for the safety population. The data will be coded using World Health Organization Drug Dictionary (WHO-DD). The summaries will be by ATC level 2 and preferred name and treatment.

### **7.8 Study Treatment Exposure**

Duration of exposure and total dosed days will be summarized in table by treatment and presented in data listing for the safety population.

## 7.9 Treatment Compliance

Compliance to Double-Blind study medication will be presented for the safety population in table by treatment.

The range 80%  $\leq$  compliance  $\leq$  120% will be used to define a subject being treatment compliant.

All study medication administration and accountability data will be listed by subject.

## 7.10 Protocol Deviations

The major protocol deviations will be summarized in tables by treatment and presented in data listings as well.

## 7.11 Efficacy Assessments

### 7.11.1 Primary Efficacy Analysis

The primary treatment comparisons of interest are the change from baseline in average daily time to first prodromal symptom associated with sunlight exposure between 1 hour post sunrise and 1 hour pre-sunset for the two MT-7117 doses (■, and ■) compared with placebo at Week 16 (Visit 8).

To assess the treatment effect at Week 16, change from baseline in average daily (minutes) time to first prodromal symptom associated with exposure to sunlight between 1 hour post sunrise and 1 hour pre-sunset at Weeks 2, 4, 6, 8, 10, 12, 14, and 16 will be analyzed using mixed-effect model for repeated-measures (MMRM).

The analysis model included fixed categorical terms for treatment, randomization strata (the baseline average daily sunlight exposure time without prodromal symptoms ( $\leq 30$  min or  $> 30$  min)), visit, and treatment by visit interaction together with continuous covariate terms for the corresponding baseline and the corresponding baseline by visit interaction. An unstructured correlation structure will be used to model the within-subject variance covariance errors. Should convergence of the model fail (due to the small numbers of subjects in this study), a Toeplitz correlation matrix will be used if appropriate, or else AR(1) correlation matrix will be used. The Kenward-Roger approximation will be used to estimate the denominator degrees of freedom. From the model described above, adjusted (least squares [LS]) means and standard errors will be produced by treatment and visit. Difference in adjusted means at each visit (each MT-7117 dose vs. placebo) with standard errors, 95% CIs and associated P-values will also be produced. All available data from all patients will be used in the primary analysis without any imputation. The figure of LS mean with standard error will be plotted from this MMRM.

A supportive analysis will be performed the same way for the primary endpoints using the PP population.

Non-parametric analysis will be performed in order to confirm the robustness for the above parametric model. The change from baseline in average daily time (minutes) to first prodromal symptom associated with exposure to sunlight between 1 hour post sunrise and

1 hour pre-sunset at each visit (Weeks 2, 4, 6, 8, 10, 12, 14 and 16) from two treatments being compared will enter the corresponding analysis. The point estimates and two-sided 95% confidence intervals for the difference between the treatment groups will be obtained using the Hodges-Lehman estimator corresponding to Wilcoxon's rank sum test. The paired comparison between each MT-7117 arm with placebo will also be performed using this non-parametric analysis method. **This non-parametric analysis will be performed with multiple imputation (MI) method in the following steps, assuming missing at random.**

**MI Step 1:** Intermittent missing values will be imputed using the Markov Chain Monte Carlo (MCMC) methodology which assumes a multivariate normal distribution over all variables included in the imputation model. The MI procedure in SAS will be used for this purpose and this first MI step is planned to be repeated 1000 times, creating different datasets with a monotone missing data structure. Seed value of 1995 will be used in the MI procedure. The following SAS code will be used to generate the monotone missing data pattern:

```
[REDACTED SAS CODE]
```

**MI Step 2:** After this, the remaining missing data will be imputed using a method for monotone missingness, also based on the MAR assumption. Thus, for each of the created dataset with a monotone missing data pattern, the MI procedure in SAS will be used to impute missing values based on a sequential procedure reflecting the monotone missing data pattern. Patients with the first missing value occurring at Week 2 will have their missing Week 2 value replaced by an imputed value from a regression model with treatment group and the baseline value as explanatory variables. In the next step, patients with their Week 4 value missing will have their missing Week 4 value replaced by an imputed value from a regression model with treatment group, baseline value and Week 2 value as explanatory variables. Similar procedure will be used to replace the missing values at Week 4, 6, 8, 10, 12, 14 and 16. The following example SAS code will be used to make the imputation with the MAR assumption:

```
[REDACTED SAS CODE]
```

**MI Step 3:** The imputed datasets generated with the approach described above do contain only non-missing values and are used as input in the model for the sensitivity analysis for the primary efficacy endpoint. The Hodges-Lehman estimator to obtain the point estimates and two-sided 95% confidence intervals for the difference between the treatment groups with paired comparison for Week 2, 4, 6, 8, 12, 14 and 16 will be run on each of the 1000 generated imputed datasets. Finally, the MIANALYZE procedure in SAS will be applied to combine the results from these analyses to derive an overall estimate of the treatment differences at Week 2, 4, 6, 8, 10, 12, 14, 16 according to the following code. In addition to the estimates, corresponding 95% confidence intervals and p-values will be calculated. The following example SAS code will be used:

[REDACTED]

The primary efficacy endpoint will also be summarized using descriptive statistics and presented in data listing.

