10.2.2 Efficacy Assessments

10.2.2.1 Analysis of Primary Efficacy Endpoints

The primary treatment comparisons of interest are the change from baseline in average daily time (**minutes**) to first prodromal symptom associated with sunlight exposure between 1 hour post sunrise and 1 hour pre-sunset for the two MT 7117 doses (■, and ■) compared with placebo at Week 16 (Visit 8). As this trial is exploratory in nature, no adjustments for multiplicity will be made.

To assess the treatment effect at Week 16, change from baseline in average daily time (**minutes**) to first prodromal symptom associated with exposure to sunlight between 1 hour post sunrise and 1 hour pre-sunset at Weeks 2, 4, 6, 8, 10, 12, 14 and 16 will be analyzed using mixed-effect model for a repeated measures (MMRM). The model will include fixed categorical terms for treatment, the baseline average daily sunlight exposure time without prodromal symptoms (≤ 30 min or >30 min), visit, and treatment by visit interaction together with continuous covariate terms for baseline average daily duration of sunlight exposure between 1 hour post sunrise and 1 hour pre-sunset without prodromal symptoms and baseline average daily duration of sunlight exposure between 1 hour post sunrise and 1 hour pre-sunset to first prodromal symptom by visit interaction. An unstructured correlation structure will be used to model the within-subject variance covariance errors. Should convergence of the model fail (due to the small numbers of subjects in this study), other variance-covariance matrices such as AR(1) correlation matrix will be used if appropriate. The Kenward-Roger approximation will be used to estimate the denominator degrees of freedom. From the model described above, adjusted (least squares [LS]) means and standard errors will be produced by treatment and visit. Difference in adjusted means at each visit (each MT-7117 dose vs. placebo) with standard errors, 95% CIs and associated P-values will also be produced. All available data from all subjects will be used in the primary analysis without any imputation.

A supportive analysis will be performed in a similar manner for the primary endpoints using the PP set.

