### 7.15.6 Subgroup Analysis

The subgroup analyses for Primary endpoints will be performed for the following subgroups using primary efficacy analysis.

- Gender (Male, Female)
- Age group (age < 65, age >= 65)
- Ethnicity (Hispanic or Latino, Non-Hispanic or Latino)
- Race (White, Black or African American, Asian, others)
- BMI (BMI <30, BMI ≥30 kg/m^2)
- Baseline average daily time to first prodromal symptom associated with exposure to sunlight (≤30 min and >30 min)
- Seasonality (Randomized between Mar 1 and Aug 31 inclusive, other)

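### If the primary MMRM falls back from unstructured, Toeplitz and AR(1) impose one variance on all visits and can misstate the Week 16 standard error

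*SAP*

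**What the plan says.** SAP section 7.11.1 fits one MMRM to change from baseline at eight time points (Weeks 2 to 16, every two weeks) and reads the primary contrasts at Week 16. The first-choice covariance is stated plainly: "An unstructured correlation structure will be used to model the within-subject variance covariance errors". A contingency follows: "Should convergence of the model fail (due to the small numbers of subjects in this study"), then "a Toeplitz correlation matrix will be used if appropriate, or else AR(1) correlation matrix will be used". Protocol section 10.2.2.1 is looser: "other variance-covariance matrices such as AR(1) correlation matrix will be used if appropriate".

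The only adjustment attached to the model is "The Kenward-Roger approximation will be used to estimate the denominator degrees of freedom". Neither document names a heterogeneous version of Toeplitz or AR(1), visit-specific variances, or a sandwich standard error. The SAS code is redacted.

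The same model serves the per-protocol analysis (7.11.1). Similar models serve many secondary and other endpoints (7.11.2). SAP section 7.15.6 adds subgroup analyses, which "will be performed for the following subgroups using primary efficacy analysis"; these include age 65 or over and four race categories.

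**The concern.** An unstructured matrix gives each visit its own variance. Standard Toeplitz and AR(1) do not: they have one variance parameter for all eight visits. A fit under either estimates something close to the average variance over Weeks 2 to 16 and uses it for the Week 16 contrast. If Week 16 is more variable than the average visit, the standard error is too small and the test rejects too often. If it is less variable, the interval is too wide and power is lost.

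Kenward-Roger adjusts for small samples under the structure that was fitted. It does not detect or repair a wrong structure. With complete data the point estimate is essentially unaffected; what suffers is the standard error, the interval and the P value. With missing data the estimate can shift as well.

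**Working it through.** **Inputs from the documents:** 8 post-baseline time points; unstructured, then Toeplitz, then AR(1) (SAP 7.11.1); 34 subjects per arm, 102 in total (SAP section 6, protocol 4.1); two-sided 5% tests (SAP 5.2). The documents state no SD, power or standard error, so there is no figure of theirs to reproduce. **Assumed:** the residual SD changes linearly from Week 2 to Week 16.

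**Covariance parameters with 8 visits**
- Unstructured: 8 × 9 / 2 = 36.
- Toeplitz: 1 variance + 7 correlations = 8. AR(1): 1 + 1 = 2.
- Heterogeneous Toeplitz: 8 + 7 = 15. Heterogeneous AR(1): 8 + 1 = 9.

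**Closed form, complete data.** The pooled SD is the root mean square (RMS) of the eight visit SDs. Let q = RMS / (SD at Week 16), the ratio of the model's standard error to the true one. The actual two-sided error rate is 2 × [1 − Φ(1.96 × q)].

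For an SD of 40 rising to 60, the mean is 50 and the step is 20/7. The variance of the eight values is (20/7)² × 63/12 = 42.86. So RMS = √(2500 + 42.86) = 50.43, q = 50.43/60 = 0.840, and the error rate is 2 × [1 − Φ(1.647)] = 10.0%. Only the ratio of the SDs matters, not the minutes chosen.

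| SD Week 2 → Week 16 (min) | Ratio | RMS | q | Actual error rate at nominal 5% |
|---|---|---|---|---|
| 60 → 40 | 0.67 | 50.43 | 1.26 | 1.4% |
| 50 → 50 | 1.0 | 50.00 | 1.00 | 5.0% |
| 50 → 60 | 1.2 | 55.10 | 0.918 | 7.2% |
| 40 → 60 | 1.5 | 50.43 | 0.840 | 10.0% |
| 40 → 80 | 2.0 | 61.41 | 0.768 | 13.2% |

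**Check against the fitted structures.** The best-fitting homogeneous AR(1) and Toeplitz were found for true correlations of AR(1) with ρ = 0.8 and compound symmetry with ρ = 0.6. The two structures agree closely. At ratio 1.5, q is 0.84 and the error rate 9.8 to 9.9%; at ratio 2.0, q is 0.77 to 0.78 and the error rate 12.9 to 13.1%. Heterogeneous AR(1) gives q = 1.00 and 5.0% at every ratio tried.

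**Check at this sample size.** REML simulation under the null: 3 arms of 34, baseline-by-visit covariate, 10% dropout (assumed), ρ = 0.8, 400 runs per setting, with a t reference on 95 df in place of Kenward-Roger. Monte Carlo standard error is about 1 point near 5% and 1.7 points near 13%.

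| Ratio | Homogeneous AR(1) | Heterogeneous AR(1) |
|---|---|---|
| 1.0 | 4.3% | 3.3% |
| 1.5 | 9.0% | 3.0% |
| 2.0 | 13.3% | 5.5% |

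At ratio 1.5 the homogeneous fit's mean standard error was 0.319 against an empirical SD of 0.367; the heterogeneous fit's was 0.381 against 0.375.

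**The case against.** **The fallback may never be used in the main analysis.** This largely stands. The SAP provides for non-convergence; a reader might infer that it expects it, but the wording is conditional. All three arms feed one 36-parameter matrix, and a 14-day window needs only one qualified diary day (SAP 5.4.1.1), so missing windows may be few. In simulated data for 102 subjects, with 10% or 25% dropout plus 3% intermittent missingness, the unstructured maximum-likelihood fit converged to a positive-definite matrix in 60 of 60 runs per setting. That used an EM algorithm, not the planned SAS procedure, and assumed dropout rates.

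**Subgroups.** It is tempting to say that the unstructured model cannot be fitted in the subgroups of SAP 7.15.6. The documents give no subgroup sizes, so that is not shown. In the same simulations the fit worked in every run with 51 subjects, and in 83% of runs with 24 subjects and 25% dropout. Failure is more likely as subgroups shrink, but a very small one may defeat a heterogeneous fit too.

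**Nothing shows that variance changes over time.** This stands as to direction. SAP section 6 says that no formal data support estimation for this endpoint, every visit averages the same length of window, and the model adjusts for baseline by visit. A reader might assume that the variance of change grows as responders separate; no passage supports it. A drug response also cannot explain false positives under the null, so the error rates above simply take unequal variance as given. Equal variance has no support in the documents either.

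**The text says correlation matrix, which might leave the variances free.** Possible, but the named structures in standard form carry one variance, and nothing in the text says otherwise.

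**There is a robustness analysis.** The planned Wilcoxon and Hodges-Lehmann analysis works visit by visit and needs no common variance across visits. It is a useful check, but it does not correct the standard error, interval or P value reported as the primary result.

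**Conclusion.** The point holds conditionally and is a modest one. If the fallback is used and the residual variance differs between visits, the Week 16 standard error is wrong and Kenward-Roger will not repair it. With a linear rise in SD by a factor of 1.2, 1.5 or 2.0, the standard error is about 8%, 16% or 23% too small and the 5% test runs at about 7%, 10% or 13%. With a fall to 0.67 it is about 26% too large. With constant variance there is no error. These ratios are assumptions; the documents fix neither size nor direction.

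One stronger reading should be resisted: that Week 16, as the last visit, is where the common variance is most wrong. In the 40 to 60 example the pooled standard error is 26% too large at Week 2 (50.43/40 = 1.26) and 16% too small at Week 16. Week 16 matters because the primary contrast is read there.

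**What to change.** In SAP section 7.11.1, set the order as:
1. unstructured;
2. heterogeneous Toeplitz (15 parameters);
3. heterogeneous AR(1) (9 parameters);
4. only if all of these fail, a homogeneous structure with an empirical (sandwich) standard error.

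Use Kenward-Roger for steps 1 to 3, and state the degrees-of-freedom rule for step 4. Replace the undefined condition about appropriateness with a concrete one, such as convergence to a positive-definite matrix, because the analysis is run after unblinding (SAP 3.2). If heterogeneous variances were already intended, saying so settles steps 2 and 3. The protocol gives AR(1) only as an example, so it does not rule out these structures.

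The cost is a line or two of SAP text and 7 extra variance parameters in a fallback fit (15 against 8, or 9 against 2). The heterogeneous fits may themselves fail in very small subgroups. Step 4 is kept so that a model is still specified there, although a sandwich standard error is also unreliable with very few subjects.

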### 7.11.2 Analysis of Secondary and Other Efficacy Endpoints

The following continuous secondary and other efficacy endpoints will be analyzed using MMRM similar to the analyses for the primary endpoint.

- Change from baseline in average daily duration (minutes) of sunlight exposure between 1 hour post sunrise and 1 hour pre-sunset without prodromal symptoms.
  - The model will include fixed categorical terms for treatment, randomization strata, visit, and treatment by visit interaction together with continuous covariate terms for baseline value and baseline value by visit interaction.
  - The figure of LS mean with standard error will be plotted.
- Change from baseline in average daily mean duration (minutes) of sunlight exposure between 1 hour post sunrise and 1 hour pre-sunset without prodromal symptoms. The daily mean duration is considered as multiple periods of sunlight exposure in each day and measurable by sum of duration of each period divided by number of periods.
  - The model will include fixed categorical terms for treatment, randomization strata, visit, and treatment by visit interaction together with continuous covariate terms for baseline value and baseline value by visit interaction.
  - The figure of LS mean with standard error will be plotted.
- Change from baseline in average daily duration (minutes) of prodromal symptoms during 16-week double-blind treatment period.
  - The model will include fixed categorical terms for treatment, randomization strata, visit, and treatment by visit interaction together with continuous covariate terms for baseline value and baseline value by visit interaction.
  - The figure of LS mean with standard error will be plotted.
- Change from baseline in average daily duration (minutes) of pain events during 16-week double-blind treatment period.
  - The model will include fixed categorical terms for treatment, randomization strata, visit, and treatment by visit interaction together with continuous covariate terms for baseline value and baseline value by visit interaction.

- The figure of LS mean with standard error will be plotted.
- Change from baseline in average daily mean intensity of the patient's prodromal symptoms during 16 week double-blind treatment period.
  - The model will include fixed categorical terms for treatment, randomization strata, visit, and treatment by visit interaction together with continuous covariate terms for baseline value and baseline value by visit interaction.
  - The figure of LS mean with standard error will be plotted.
- Change from baseline in average daily mean intensity of the patient's pain events during 16 week double-blind treatment period.
  - The model will include fixed categorical terms for treatment, randomization strata, visit, and treatment by visit interaction together with continuous covariate terms for baseline value and baseline value by visit interaction.
  - The figure of LS mean with standard error will be plotted.
- Change from baseline for all total score and total score in each domain of Physical Function, Anxiety, Depression, Fatigue, Sleep Disturbance, Ability to Participate in Social Roles and Activities, Pain Interference, Pain intensity in PROMIS-57.
  - The model will include fixed categorical terms for treatment, randomization strata, visit, and treatment by visit interaction together with continuous covariate terms for baseline value and baseline value by visit interaction.
  - The figure of LS mean with standard error will be plotted by all total score and total score in each domain of PROMIS-57.
- PGIC
  - The model will include fixed categorical terms for treatment, randomization strata, visit, and treatment by visit interaction.
  - The figure of LS mean with standard error will be plotted.

The following secondary endpoint will be listed and summarized by treatment and planned time point using descriptive statistics. The value of melanin density, change from baseline and % change from baseline in melanin density at Week 8, 16, and 22 by skin segments and average of 6 skin segments will be plotted by treatment. For average of 6 skin segments for the value of melanin density, change from Baseline and % change from baseline in melanin density at Week 8, 16, and 22, will be analyzed using MMRM similar to the analyses for the primary endpoint.

- The change from baseline and % change from baseline in melanin density at Week 8, 16, and 22 by skin segments.
- Average of 6 skin segments for the change from Baseline and % change from baseline in melanin density at Week 8, 16, and 22.

The value of melanin density, change from baseline and % change from baseline in melanin density at Week 8, 16, and 22 by skin segments and average of 6 skin segments will be plotted by treatment.

The following endpoints will be analyzed using a negative binomial regression model with log link will be fitted. The model will include treatment and the baseline average daily sunlight exposure time without prodromal symptoms ( $\leq 30$  min or  $> 30$  min) as fixed effect, and baseline total number of sunlight exposure episodes with prodromal symptoms as the covariate. The estimated incidence rate (IR) and its 95% confidence interval for each treatment group, incidence rate ratio (IRR) of each active MT-7117 treatment group versus placebo, 95% confidence interval of the IRR together with relevant p-values will be reported.

- Total number of sunlight exposure episodes with prodromal symptoms during 16-week double-blind treatment period.
- Total number of pain events during 16-week double-blind treatment period.

The following example SAS code will be used;

```
[REDACTED SAS CODE]
```

The following endpoints will be summarized using descriptive statistics and Wilcoxon's rank sum test.

- Total number of days subject is exposed to sunlight for any duration between 1 hour post sunrise and 1 hour pre-sunset without prodromal symptoms during 16-week double-blind treatment period.

The following endpoint will be analyzed using ANCOVA or ANOVA model.

- Change from baseline for In-clinic sunlight exposure time (minutes) to the first prodromal symptoms.
  - The model will include fixed categorical terms for treatment, randomization strata, together with continuous covariate terms for baseline value.
- Change from baseline in Average daily duration (minutes) of sunlight exposure between 1 hour post sunrise and 1 hour pre-sunset on Saturday without prodromal symptoms at Week 16. The average value is calculated for Saturdays within the windows defined in section 5.4.
  - The model will include fixed categorical terms for treatment, randomization strata, together with continuous covariate terms for baseline value.
- Change from baseline in average daily duration of sunlight exposure regardless of time of day without prodromal symptoms assessed at Week 16
  - The model will include fixed categorical terms for treatment, randomization strata, together with continuous covariate terms for baseline value.

- Total time (hours) during 16-week double-blind treatment period in duration of sunlight exposure between 1 hour post sunrise and 1 hour pre-sunset without prodromal symptoms.
  - The model will include fixed categorical terms for treatment, randomization strata.

